**Table 8** **Laboratory Safety Variables**

Haematology/haemostasis (whole blood)	Clinical chemistry (serum or plasma)
Haemoglobin	Creatinine a
Leukocyte count	Bilirubin, total
Leukocyte differential count (absolute count) b	Alkaline phosphatase
Platelet count	AST
Absolute neutrophil count	ALT
Absolute lymphocyte count	Albumin
Total white blood cell count	Potassium
Total red blood cell count	Calcium, total
	Sodium
	Creatine kinase c
	Amylase
	Magnesium
Urinalysis d	Gamma-glutamyl transferase
Haemoglobin/Erythrocytes/Blood	Protein, total
Protein/Albumin	Urea /blood urea nitrogen g
Glucose	Coagulation variables (aPTT, PTT, and INR) e
	Phosphate
	Troponin f

a Creatinine clearance and glomerular filtration rate to be calculated at screening and if clinically indicated.

b If absolute count is unavailable per site practice, % /ratio can be entered.

c Creatine kinase to be assessed in accordance with the schedule of activities and if unexplained muscle weakness or myalgia (muscle pain) occurs see Section 8.2.1 for additional information.

d Urine microscopy will be assessed if other urinalysis measurements are abnormal or if clinically indicated.

e Coagulation variables to be assessed at screening and if clinically indicated. If both aPTT and PTT tests are not performed per local laboratory it is acceptable to enter the results for the test which is performed and leave the other test result as blank/ not done. If INR is not available per site practice, Prothrombin time can be entered.

f Troponin (isoform per site norm), should be assessed at screening, and performed when there is a significant drop in LVEF (of  $\geq 10$  percentage points relative to baseline and to an absolute LVEF below the institution's LLN on study intervention) or for any cardiorespiratory events with no obvious diagnosis. If troponin assessments are not available, per local practice, CK-MB isoform should be assessed. Participants should be managed according to the algorithm provided in [Appendix H](#).

g Urea or blood urea nitrogen based on local site practice.

ALT, alanine aminotransferase; aPTT, activated partial thromboplastin time; AST, aspartate aminotransferase; CK MB, creatine kinase-myocardial band; INR, international normalised ratio; LLN, lower limit of normal; LVEF, left ventricular ejection fraction PTT, partial thromboplastin time.

The investigator should assess the available results with regard to clinically relevant abnormalities in documentation. Any clinically significant abnormal laboratory values should be repeated as clinically indicated and recorded on the eCRF. Situations in which laboratory safety results should be reported as AEs are described in Section 8.3.5.

All participants with Grade 3 or 4 laboratory values at the time of completion or discontinuation from study intervention must be followed and have further tests performed until the laboratory values have returned to Grade 1 or 2, unless these values are not likely to improve because of the underlying disease.

**NB.** In case a participant shows an AST **or** ALT  $\geq 3 \times$  ULN together with TBL  $\geq 2 \times$  ULN please refer to [Appendix E](#) “Actions required in cases of increases in liver biochemistry and evaluation of HL”, for further instructions.

### **8.2.7 Ophthalmologic Examinations**

An ophthalmologic examination (best corrected visual acuity, IOP and slit-lamp fundoscopy) will be evaluated at the times outlined in the SoA, and as clinically indicated whilst the participant is on study intervention. The participant should be examined using the same machine and operator throughout the study wherever possible.

If a participant experiences symptoms of visual disturbance (including blurring of vision), a complete ophthalmological examination, including a slit-lamp examination, must be performed. If an abnormality is detected, fundus photography and an optical coherence tomography scan can also be performed where required. Adverse events are to be managed according to [Appendix H](#).

If a retinal abnormality prior to or at the time of selumetinib discontinuation is observed, a repeat ophthalmological examination is to be performed 30 days after discontinuation of selumetinib in order to document reversibility. Abnormalities should be followed up.

### **8.2.8 Other Safety Assessments**

#### **8.2.8.1 ECOG Performance Status**

ECOG performance status will be assessed at the times specified in the SoA based on the following:

- 0 Fully active; able to carry out all usual activities without restrictions.
- 1 Restricted in strenuous activity, but ambulatory and able to carry out light work or work of a sedentary nature (eg, light housework or office work).
- 2 Ambulatory and capable of self-care, but unable to carry out any work activities; up and about more than 50% of waking hours.
- 3 Capable of only limited self-care; confined to bed or chair more than 50% of waking hours.
- 4 Completely disabled; unable to carry out any self-care and totally confined to bed or chair.
- 5 Dead

Any significant change from baseline or screening must be reported as an AE.

### **8.3 Adverse Events and Serious Adverse Events**

The principal investigator is responsible for ensuring that all staff involved in the study are familiar with the content of this section.

The definitions of an AE or SAE can be found in [Appendix B](#).

Adverse events will be reported by the participant (or, when appropriate, by a caregiver, surrogate, or the participant's legally authorised representative).

The investigator and any designees are responsible for detecting, documenting, recording, and reporting events that meet the definition of an AE.

#### **8.3.1 Time Period and Frequency for Collecting AE and SAE Information**

Adverse events and SAEs will be collected from the time of signature of the ICF, throughout the treatment period and until the follow-up period is completed. Collection and reporting of AEs and SAEs after the final DCO is described in Section [8.3.11](#).

If the investigator becomes aware of an SAE with a suspected causal relationship to the study intervention that occurs after the end of the clinical study in a participant treated by him or her, the investigator shall, without undue delay, report the SAE to AstraZeneca.

#### **8.3.2 Follow-up of AEs and SAEs**

Any AEs that are unresolved at the participant's last AE assessment in the study are followed up by the investigator for as long as medically indicated, but without further recording in the eCRF. AstraZeneca retains the right to request additional information for any participant with ongoing AE(s)/SAE(s) at the end of the study, if judged necessary.

#### **Adverse Event Variables**

The following variables will be collected for each AE:

- AE (verbatim).
- The date when the AE started and stopped.
- The CTCAE grade and changes in CTCAE grade.
- Whether the AE is serious or not ([Appendix B](#)).
- Investigator causality rating against the study intervention(s) (yes or no).
- Action taken with regard to study intervention(s).
- AE caused participant's withdrawal from study (yes or no).

- Administration of treatment for the AE.
- Outcome.

In addition, the following variables will be collected for SAEs:

- Date AE met criteria for SAE.
- Date investigator became aware of SAE.
- Seriousness criteria.
- Date of hospitalisation.
- Date of discharge.
- Probable cause of death.
- Date of death.
- Autopsy performed.
- Causality assessment in relation to study procedure(s).
- Causality assessment to other medication.

The grading scales found in the National Cancer Institute CTCAE (Version 5.0) will be utilised for all events with an assigned CTCAE grading. For those events without assigned CTCAE grades, the recommendation in the CTCAE criteria that converts mild, moderate, and severe events into CTCAE grades should be used. A copy of the CTCAE can be downloaded from the Cancer Therapy Evaluation Program website (<http://ctep.cancer.gov>).

### **8.3.3 Causality Collection**

The investigator should assess causal relationship between study intervention and each AE, and answer “yes” or “no” to the question “Do you consider that there is a reasonable possibility that the event may have been caused by the investigational product?”

For SAEs, causal relationship should also be assessed for other medication and study procedures. Note that for SAEs that could be associated with any study procedure the causal relationship is implied as “yes”.

A guide to the interpretation of the causality question is found in [Appendix B](#) to the CSP.

### **8.3.4 Adverse Events Based on Signs and Symptoms**

All AEs spontaneously reported by the participant or reported in response to the open question from the study site staff: “Have you had any health problems since the previous visit/you were last asked?”, or revealed by observation will be collected and recorded in the eCRF. When collecting AEs, the recording of diagnoses is preferred (when possible) to recording a list of

signs and symptoms. However, if a diagnosis is known and there are other signs or symptoms that are not generally part of the diagnosis, the diagnosis and each sign or symptom will be recorded separately.

### **8.3.5 Adverse Events Based on Examinations and Tests**

The results from the CSP-mandated laboratory tests, vital signs, physical examinations, ECGs, and ECHO/cardiac MRI scans will be summarised in the Clinical Study Report.

Deterioration as compared with baseline in protocol-mandated laboratory values, vital signs, physical examinations, ophthalmologic examinations, ECGs and ECHO/cardiac MRI should therefore only be reported as AEs if they fulfil any of the SAE criteria, are the reason for discontinuation of treatment with the study intervention or are considered to be clinically relevant as judged by the investigator (which may include but not limited to consideration as to whether treatment or non-planned visits were required or other action was taken with the study intervention, eg, dose adjustment or study intervention interruption).

If deterioration in a laboratory value/vital sign/ECG/ECHO or cardiac MRI is associated with clinical signs and symptoms, the sign or symptom will be reported as an AE and the associated laboratory result/vital sign/ECG/ECHO or cardiac MRI will be considered as additional information. Wherever possible the reporting investigator uses the clinical, rather than the laboratory term (eg, anaemia versus low haemoglobin value). In the absence of clinical signs or symptoms, clinically relevant deteriorations in non-mandated parameters should be reported as AE(s).

Deterioration of a laboratory value, which is unequivocally due to PD, should not be reported as an AE/SAE.

Any new or aggravated clinically relevant abnormal medical finding at a physical examination as compared with the baseline assessment will be reported as an AE unless unequivocally related to the disease under study.

### **8.3.6 Hy's Law**

Cases where a participant shows elevations in liver biochemistry may require further evaluation and occurrences of AST or ALT  $\geq 3 \times$  ULN together with TBL  $\geq 2 \times$  ULN may need to be reported as SAEs. Please refer to [Appendix E](#) for further instruction on cases of increases in liver biochemistry and evaluation of HL.

### **8.3.7 Disease Progression**

Disease progression can be considered as a worsening of a participant's condition attributable to the disease for which the study intervention is being studied. It may be an increase in the severity of the disease under study and/or increases in the symptoms of the disease. The

development of new symptoms, or the progression of existing symptoms, of NF1-PN should be considered as PD and not an AE. Events, which are unequivocally due to PD, should not be reported as an AE during the study.

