### **8.3.8 Disease Under Study**

Symptoms of the disease under study are those which might be expected to occur as a direct result of NF1-PN. Events which are unequivocally due to disease under study should not be reported as an AE during the study unless they meet SAE criteria or lead to discontinuation of the study intervention.

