### 8.3.12 Reporting of Serious Adverse Events

All SAEs have to be reported, whether or not considered causally related to the study intervention, or to the study procedure(s). All SAEs will be recorded in the eCRF.

If any SAE occurs in the course of the study, then investigators or other site personnel inform the appropriate AstraZeneca representatives within one day ie, immediately but **no later than 24 hours** of when he or she becomes aware of it.

The designated AstraZeneca representative works with the investigator to ensure that all the necessary information is provided to the AstraZeneca Patient Safety data entry site **within**

**one calendar day** of initial receipt for fatal and life-threatening events **and within 5 calendar days** of initial receipt for all other SAEs.

For fatal or life-threatening AEs where important or relevant information is missing, active follow-up is undertaken immediately. Investigators or other site personnel inform AstraZeneca representatives of any follow-up information on a previously reported SAE within one calendar day ie, immediately but **no later than 24 hours** of when he or she becomes aware of it. Note: In Germany SAE reporting has to be done immediately without undue delay after obtaining knowledge.

Once the investigators or other site personnel indicate an AE is serious in the EDC system, an automated email alert is sent to the designated AstraZeneca representative.

If the EDC system is not available, then the investigator or other study site staff reports a SAE to the appropriate AstraZeneca representative by telephone followed by completion of a paper SAE form.

The AstraZeneca representative will advise the investigator/study site staff how to proceed.

For further guidance on the definition of a SAE, see [Appendix B](#) of the CSP.

The reference document for definition of expectedness/listedness is the IB for selumetinib.

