## **Appendix B Adverse Events: Definitions and Procedures for Recording, Evaluating, Follow-up, and Reporting**

### **B 1 Definition of Adverse Events**

An AE is the development of any untoward medical occurrence (other than progression of the disease under evaluation) in a participant or clinical study participant administered a study intervention and which does not necessarily have a causal relationship with this treatment. An AE can therefore be any unfavourable and unintended sign (eg, an abnormal laboratory finding), symptom (for example nausea, chest pain), or disease temporally associated with the use of a medicinal product, whether or not considered related to the study intervention.

The term AE is used to include both serious and non-serious AEs and can include a deterioration of a pre-existing medical occurrence. An AE may occur at any time, including run-in or washout periods, even if no study intervention has been administered.

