### **B 2 Definitions of Serious Adverse Event**

An SAE is an AE occurring during any study phase (ie, run-in, treatment, washout, follow-up), that fulfils one or more of the following criteria:

- Results in death.
- Is immediately life-threatening.
- Requires in-participant hospitalisation or prolongation of existing hospitalisation.
- Results in persistent or significant disability or incapacity.
- Is a congenital anomaly or birth defect.
- Is an important medical event that may jeopardise the participant or may require medical treatment to prevent one of the outcomes listed above.

Adverse events of **malignant tumours** reported during a study should generally be assessed as **Serious** AEs. If no other seriousness criteria apply, the “Important Medical Event” criterion should be used. In certain situations, however, medical judgment on an individual event basis should be applied to clarify that the malignant tumour event should be assessed and reported as a **Non-Serious** AE. For example, if the tumour is included as medical history and progression occurs during the study, but the progression does not change treatment and/or prognosis of the malignant tumour, the AE may not fulfil the attributes for being assessed as serious, although reporting of the progression of the malignant tumour as an AE is valid and should occur. Also, some types of malignant tumours, which do not spread remotely after a routine treatment that does not require hospitalisation, may be assessed as Non-Serious; examples in adults include Stage 1 basal cell carcinoma and Stage 1A1 cervical cancer removed via cone biopsy.

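### Protocol Sections 8.3.7 and 8.3.8 give opposite AE-reporting rules for an event due to worsening NF1-PN that is serious or leads to discontinuation, and nothing says which prevails

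*Protocol*

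**What the plan says.** Protocol Section 8.3.7 (Disease Progression) says that the "development of new symptoms, or the progression of existing symptoms, of NF1-PN should be considered as PD and not an AE". It then adds: "Events, which are unequivocally due to PD, should not be reported as an AE during the study". Neither sentence makes an exception for a serious event or for one that stops treatment.

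Section 8.3.8 (Disease Under Study) follows directly. It sets its scope as follows: "Symptoms of the disease under study are those which might be expected to occur as a direct result of NF1-PN". Events unequivocally due to that disease "should not be reported as an AE during the study unless they meet SAE criteria or lead to discontinuation of the study intervention".

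Section 8.3.12 states: "All SAEs have to be reported, whether or not considered causally related to the study intervention". Appendix B 1 begins its definition of an AE with "any untoward medical occurrence (other than progression of the disease under evaluation", so progression is carved out at the start, and it adds: "The term AE is used to include both serious and non-serious AEs". Appendix B 2 says: "An SAE is an AE occurring during any study phase".

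SAP Section 3.3.2.4 makes the analysis of randomised-period treatment-emergent AEs a comparison of the two arms. SAP Section 4.6.2.2 lists tables of SAEs and of AEs leading to discontinuation for that period.

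**The concern.** Participants are symptomatic at entry. Protocol Section 4.1 names pain, airway impairment and motor, bowel or bladder dysfunction among the symptoms. A worsening that leads to admission or to stopping study drug is therefore a realistic event, and it is one on which two adjacent sections disagree.

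A site that follows 8.3.7 files nothing. A site that follows 8.3.8 files an SAE, or an AE leading to discontinuation. The SAP tabulates what is reported and has no rule for identifying, adding or removing progression-related events, so mixed practice passes straight into the tables. There is no IDMC (Protocol Section 9.6). Ongoing sponsor monitoring (Appendix A 5) can act only on what sites send.

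**Working it through.** The plan gives no figure on this point to reproduce. The check sets the rules side by side and then shows scale.

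**1. A test event.** Take a participant admitted to hospital because existing plexiform neurofibroma pain has worsened, unequivocally because of the neurofibroma.

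| Question | Section 8.3.7 | Section 8.3.8 |
|---|---|---|
| Is the event in scope? | Yes: progression of an existing NF1-PN symptom counts as PD | Yes: a symptom arising directly from NF1-PN |
| Is there an exception for serious events? | No | Yes |
| Is there an exception for discontinuation? | No | Yes |
| Result for the admission | Not reported | Reported as an SAE |
| Result if it instead led to stopping study drug | Not reported | Reported as an AE leading to discontinuation |

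**2. Can the two be read together?**

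- *8.3.7 bars only non-serious AEs.* This fails. Appendix B 1 says that the term AE covers serious and non-serious events, and B 2 makes every SAE an AE first. If an event is not an AE, it is not an SAE.
- *8.3.7 is for progression and 8.3.8 is for stable disease.* This fails. 8.3.7 defines progression to include worsening symptoms, and a worsened NF1-PN symptom is also a direct result of NF1-PN.

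**3. Does another section decide?**

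- Appendix B 1 excludes progression from the AE definition, and the laboratory sentence in 8.3.5 says that deterioration unequivocally due to PD is neither an AE nor an SAE. Both agree with 8.3.7.
- Appendix B 3 tells investigators how to rate causality when the disease has deteriorated for lack of effect. That presupposes that some such events are reported, which leans towards 8.3.8.
- 8.3.12 requires every SAE to be reported but does not say whether a serious progression event is an SAE. Under B 1 and B 2 it might not be.
- 8.3.9 deals with deaths from an AE or from an unknown cause. It gives no route for a death due to progression.

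None of these says which section prevails.

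**4. Scale.** The input is 73 participants per arm (Protocol Section 9.2). If *m* participants in an arm have such an event as their only SAE, moving from one rule to the other changes that arm's SAE percentage by 100 × *m*/73.

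- *m* = 1: 100 × 1/73 = 1.4 points.
- *m* = 5: 100 × 5/73 = 6.8 points.

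The range 1 to 5 is an assumption, because the documents give no expected number.

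The change in the difference between arms is 100 × (*m* on placebo − *m* on selumetinib)/73. With equal numbers it is zero. With an assumed 5 against 1 it is 100 × 4/73 = 5.5 points. The direction and size therefore depend wholly on an imbalance that the documents do not quantify.

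**The case against.** The strongest reply is that this is a wording matter of limited reach, and much of that stands. Both rules turn on events unequivocally due to the disease, and the conflict bites only when such an event is serious or stops treatment. Safety is summarised descriptively (Protocol Section 9.4.3). The randomised period is blinded, and a site's reading applies to participants in both arms, so mixed practice does not by itself bias the comparison. Discontinuations for progression are not lost: the reason goes into the eCRF (Protocol Section 7.1) and disposition is tabulated by reason, including before the end of Cycle 12 (SAP Section 4.1.1.2). Events may also be few. SAP Section 4.2.16.1 analyses randomised-period PFS only if at least 5 progressions or deaths occur across both arms. None of this removes the contradiction.

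A reader might infer three stronger things that the documents do not support.

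- *The safety comparison is biased because placebo participants will have more of these events.* That is plausible, but no rate is given for either arm.
- *8.3.7 departs from a protocol in which PD is otherwise always a volumetric REiNS finding, so pointing it to REiNS would settle the matter.* Sections 6.7 and 7.1 use investigator-judged progression, and 8.1.1 bases participant management on the investigator's own assessments. Central review results are in general not sent to investigators (8.1.1), so a site could not apply that definition within the 24-hour SAE reporting limit in 8.3.12.
- *8.3.12 already makes these events reportable.* It governs SAEs once an event is one, and the dispute is whether it is.

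**Conclusion.** The concern holds as an internal contradiction between two stated rules. For an event unequivocally due to worsening NF1-PN that is serious or leads to discontinuation, 8.3.7 says not to report it and 8.3.8 says to report it. Sites have no basis in the protocol for choosing.

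The consequence is confined to safety reporting: the SAE and AE-leading-to-discontinuation tables, and any death or grade 3 or higher rows that contain the same events. The primary endpoint, both key secondary endpoints and the multiple testing procedure are untouched.

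The total effect cannot be sized from the documents. The 1.4 points per affected participant assumes 73 treated per arm and no other SAE in that participant. An effect on the arm difference also needs an imbalance in progression, which is an assumption. The point is worth correcting because serious events may go unreported and the correction is cheap. It does not threaten the trial's efficacy conclusions.

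**What to change.** Reconcile 8.3.7 and 8.3.8 so that one rule covers events due to NF1-PN progression that are serious or lead to discontinuation. One way is for 8.3.7 to state explicitly whether the 8.3.8 exception applies to it. Changing 8.3.7 alone is not enough. The laboratory sentence in 8.3.5, the death rules in 8.3.9, the SAE rule in 8.3.12 and the definitions in Appendix B 1 and B 2 must be aligned with whichever rule is chosen. Sites should then receive a memo giving the rule and a worked example.

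The cost is a short protocol clarification across those sections and the memo. If the exception is carried into 8.3.7, there will be slightly more SAE reports. No analysis or sample size changes.
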